### **3 STUDY OBJECTIVE(S) AND DESIGN**

#### **3.1 Study Objective(s)**

The study objective is to evaluate the seizure rate and monitor the safety of enzalutamide treatment in subjects with metastatic castration-resistant prostate cancer known to have risk factor(s) for seizure.

#### **3.2 Study Design**

This is a multicenter, single-arm, open-label, post-marketing safety study to evaluate the risk of seizure among subjects with metastatic castration-resistant prostate cancer (mCRPC) treated with enzalutamide who are at potential increased risk of seizure.

Subjects will be enrolled into the study and participate in a 4-month treatment period of enzalutamide (160 mg/day). At the end of the 4-month treatment visit, subjects who are assessed as deriving benefit from enzalutamide treatment may continue in the extension period. Data will be collected in the extension period for each subject per the Schedule of Assessments for a period of one year after the 4-month treatment visit or 30 days post discontinuation during the one year timeframe.

When any subject who continues on treatment after his 12-month extension period, data collection will be limited to dosing information, serious adverse events (SAEs), AEs Grade 3 or higher that are drug related, and AEs of special interest or that lead to discontinuation.

Each subject will be given a patient card with the following information; a list of signs and symptoms of a suspected seizure (Seizure Description Subject Information) and a Suspected Seizure Event Questionnaire list as well as instructions regarding what to do in the event of a suspected seizure for awareness.

#### **3.3 Randomization**

This is a single-arm study and no randomization is considered.

### **4 SAMPLE SIZE**

Approximately four hundred (400) subjects will be enrolled to target approximately 350 evaluable subjects, assuming a drop-out rate of approximately 13% for this population and based on the recommendation from the FDA, respectively. Assuming the true incidence of seizure as 1% and the sample size of 350, the chance of observing 5 or less subjects with seizure events is 85.9%. Given 5 out of 350 subjects, i.e., point estimate of 1.43%, the upper limit 95% exact confidence interval will be 3.31% and the width of the exact confidence interval will be 2.84%.

## **5 ANALYSIS SETS**

In accordance with International Conference on Harmonization (ICH) recommendations in guidelines E3 and E9, the following analysis sets will be used for the analyses.

Detailed criteria for analysis sets will be laid out in Classification Specifications (CS) and the allocation of subjects to analysis sets will be determined prior to database hard lock.

### **5.1 Safety Analysis Set (SAF)**

The Safety Analysis Set (SAF) consists of all randomized subjects who received at least one dose of study drug and for whom any data is reported after first dose of study drug.

The SAF will be used for summaries of demographic and baseline characteristics and all safety and tolerability related variables.

### **5.2 Seizure Risk Evaluation Set (SRES)**

For the statistical summary and analysis of seizure events, seizure risk evaluation set (SRES) will be used by including all evaluable subjects. An evaluable subject is defined as a subject with a confirmed seizure during the 4-month treatment period of the study or who completed at least 3 months (75%) of the planned treatment.

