7.2.2 Seizure Risk Evaluation Set (SRES)

For the statistical summary and analysis of seizure events, seizure risk evaluation set (SRES) will be used by including all evaluable subjects. An evaluable subject is defined as a subject with a confirmed seizure during the 4-month treatment period of the study or who completed at least 3 months (75%) of the planned treatment.

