7.4.1 Analysis of Primary Endpoint

7.4.1.1 Primary Analysis

Primary endpoint, the proportion of evaluable subjects with at least one confirmed seizure as adjudicated by the IAC during the 4-month treatment duration will be analyzed estimated using point estimate and its 95% exact confidence interval using all SRES.

In case the drop-out rate is higher than expected, appropriate method such as Kaplan-Meier estimations [Kaplan and Meier, 1958; Greenwood, 1926] may be considered to efficiently estimate the proportion of seizure events with accounting for the censored observations in the SAF.

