### **6.2 Safety Variables**

#### **6.2.1 Primary Endpoint**

The proportion of subjects in SRES with at least one confirmed seizure as adjudicated by the Independent Adjudication Committee (IAC) during the 4-month treatment duration.

An evaluable subject is defined as a subject with a confirmed seizure during the 4-month treatment period of the study or who completed at least 3 months (75%) of the planned treatment. Only an enrolled subject who discontinues the study before completing 3 months on treatment may be replaced at the discretion of the Sponsor, however, an enrolled subject who is discontinued due to a confirmed seizure event will not be replaced.

A cumulative summary to include all seizure events, including those occurring beyond the 4 month treatment period will be included.

In case the drop-out rate is higher than expected, appropriate method such as Kaplan-Meier estimations may be considered.

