### **7.2 Study Population**

#### **7.2.1 Disposition of Subjects**

The following subject data will be presented:

- Number and percentage of subjects in each analysis set;
- Number and percentage of subjects completed and discontinued 4 month treatment period, by primary reason for treatment discontinuation;
- Number and percentage of subjects completed and discontinued the 1 year extension period, by primary reason for discontinuation; and

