### **7.5.1 Analysis of Primary Endpoint**

#### **7.5.1.1 Primary Analysis**

Primary endpoint, the proportion of evaluable subjects with at least one confirmed seizure as adjudicated by the IAC during the 4-month treatment duration, will be estimated using point estimate and its 95% exact confidence interval using all SRES.

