#### **7.5.1.2 Secondary Analysis**

The same analysis of the primary endpoint as described in 7.5.1.1 will be conducted for a cumulative proportion to include all seizure events, including those occurring beyond the 4 month-treatment period using all SRES. Incidence of seizure events, including only the first seizure event, per patient-time exposure will be summarized for SAF. Any subsequent seizure event(s) will be listed.

In addition, seizure event free rate at 4 months, 12 months, and 16 months will be calculated using Kaplan-Meier estimation if data permit in SAF.

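### Does counting early leavers only if they had a seizure bias the primary proportion enough to need a change?

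*SAP*

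**What the plan says.** Protocol 7.2.2 and SAP 5.2 share one definition of an evaluable subject: anyone who had "a confirmed seizure during the 4-month treatment period of the study or who completed at least 3 months (75%) of the planned treatment". SAP 7.5.1.1 fixes the primary analysis without condition: the proportion "will be estimated using point estimate and its 95% exact confidence interval using all SRES".

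Kaplan-Meier estimation appears in two roles:

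- **Contingency.** Protocol 7.4.1.1 says "In case the drop-out rate is higher than expected, appropriate method such as Kaplan-Meier estimations" may be used in the SAF. SAP 6.2.1 repeats this ("appropriate method such as Kaplan-Meier estimations may be considered") without naming a set. Neither gives a threshold. The only reference value is the planning figure in SAP 4, "assuming a drop-out rate of approximately 13% for this population".
- **Secondary analysis.** SAP 7.5.1.2 says the "seizure event free rate at 4 months, 12 months, and 16 months will be calculated using Kaplan-Meier estimation if data permit in SAF". The same section commits, with no proviso, to first-seizure incidence per patient-time in the SAF.

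SAP 7.2.1 also reports the size of each analysis set and the "Number and percentage of subjects completed and discontinued 4 month treatment period, by primary reason for treatment discontinuation". SAP 7.3.1 tabulates exposure, with a category for under 3 months.

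**The concern.** Take two men who both stop at week 8. The one with a confirmed seizure enters the numerator and the denominator. The one without is removed from both. Early leavers can therefore only raise the proportion, and if leaving is unrelated to seizure risk the crude SRES figure is biased upward.

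The natural check is an estimate that uses early leavers' follow-up up to the time they stop. That estimate is described in one place as a contingency and in another as a secondary analysis subject to the data allowing it. The trial is open-label, Protocol 7 lets the SAP be finalised as late as soft lock, and SAP 1 allows revision up to hard lock. On the wording alone, the prominence of the check could be settled after drop-out and seizures are known. At stake would be a misstated 4-month seizure risk, with the correcting analysis left to discretion.

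**Working it through.** **Inputs from the documents.** Seizure rate 2.8 per 100 patient-years (Protocol 7.1), so λ = 0.028/12 = 0.002333 per month. 400 enrolled, about 350 evaluable, drop-out about 13% (Protocol 7.1, SAP 4).

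**Assumptions, not in the documents.** Constant seizure hazard; drop-out independent of seizure; the whole 13% leave before month 3. Their timing is varied: all at day 0, uniform over months 0 to 3, or all just before month 3.

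**1. The plan's own figures.** P(X ≤ 5) with n = 350 is 0.8586 at 1% (SAP: 85.9%) and 0.8892 at 0.93% (protocol: 88.9%). The exact 95% interval for 5/350 is 0.47% to 3.30%, width 2.84 points; the documents give an upper limit of 3.31%, a rounding difference. 400 × 0.87 = 348. The figures reproduce.

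**2. True 4-month risk.** F(t) = 1 − exp(−λt), so F(4) = 1 − exp(−0.009333) = 0.929%.

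**3. Expected SRES proportion.** With d the early drop-out fraction and E the chance that an early leaver has a seizure before leaving,

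SRES = [d·E + (1 − d)·F(4)] / [d·E + (1 − d)].

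E is 0 for day 0, F(3) = 0.698% for month 3, and 1 − F(3)/(3λ) = 1 − 0.0069756/0.007 = 0.349% for uniform timing. For d = 13%, uniform: numerator 0.13 × 0.003492 + 0.87 × 0.009290 = 0.008536; denominator 0.000454 + 0.87 = 0.870454; ratio 0.981%.

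| Early drop-out | day 0 | uniform | month 3 |
|---|---|---|---|
| 13% | 0.929% (0) | 0.981% (+5.6%) | 1.032% (+11.1%) |
| 30% (assumed) | 0.929% (0) | 1.077% (+15.9%) | 1.224% (+31.8%) |

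At 13% the largest excess is 1.032 − 0.929 = 0.103 point. Expected seizures among the 52 early leavers (0.13 × 400) are 0, 0.18 or 0.36. In simulation with 400 subjects, the exact SRES interval covered the true risk in about 97% to 98% of trials at 13%, and in 93.9% to 98.4% at 30%.

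**4. If seizures up to 30 days off drug count.** Step 3 stops observation at leaving, but Protocol 5.4.2 collects serious adverse events, and hence all potential seizures (Protocol 5.5.2), until 30 days after the last dose. Adding one month of observation makes E equal to F(1) = 0.233%, 0.581% or F(4) = 0.929%. At 13% the SRES expectation becomes 0.963%, 1.015% or 1.066% (+3.7%, +9.3%, +14.8%). The largest excess is 0.137 point.

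**5. Effects in the other direction.** Subjects who leave in months 3 to 4 stay in the denominator with incomplete follow-up. If a further 10% do so (observation ending at leaving), the 13% row becomes −1.4%, +4.1%, +9.7%. If drop-out is informative (assumed: 25% of subjects have three times the hazard and leave early at 40% versus 4%, uniform timing), the SRES figure is 0.9% too low and Kaplan-Meier 6.2% too low. The sign is not fixed.

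**6. What the Kaplan-Meier check adds.** Under independent drop-out at 13% by month 3, its simulated mean was 0.928% against 0.929%. It relies on the independence that would be in doubt if drop-out were informative. Censoring deaths places it 1.5% to 4.2% above cumulative incidence if 3% to 8% die by month 4 (assumed).

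**The case for a change.** The strongest case for a change is that the role of the Kaplan-Meier estimate is unsettled. Protocol 7.4.1.1 places it under the primary analysis, SAP 7.5.1.1 omits it, SAP 7.5.1.2 makes it secondary, and the two provisos differ and lack thresholds. If early drop-out reached 30%, the relative bias could be +16% to +32% (observation ending at leaving), so the check would matter most when its use is least certain.

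The observation about wording stands. What follows from it is limited:

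- The primary set and estimator are fixed, so any late discretion touches only a supportive estimate.
- SAP 7.5.1.2 states that the 4-month rate will be calculated. Its proviso covers three time points and reads as a feasibility caveat, which any version would need: with no seizures (2.5% to 3.9% of simulated trials at 13%) Kaplan-Meier gives no usable interval.
- First-seizure incidence per patient-time in the SAF carries no proviso and uses early leavers' follow-up, though it is not confined to 4 months.
- Replacing the contingency in Protocol 7.4.1.1 and SAP 6.2.1 with a fixed sensitivity estimate would remove the route to another method when drop-out is high. It would also require a protocol amendment under Protocol 8.3.3.

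The SAP does not state the censoring time for the 4-month estimate. That is ordinary detail for the table and data specifications to which SAP 7.1 and 7.10 refer.

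**Conclusion.** SRES membership does depend on the outcome, and under independent early drop-out the primary proportion is slightly high. At the planned 13% and 2.8 per 100 patient-years the excess is 0 to 0.10 percentage point if observation ends at leaving, and up to about 0.14 if seizures within 30 days off drug count. The planned interval is 2.84 points wide and its coverage at 13% stays at about 97% or above (observation ending at leaving). The direction is not guaranteed if many leave in months 3 to 4 or if drop-out is related to seizure risk.

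The study is a single-arm estimation with no direct comparison planned (Protocol 1.1), and no stated decision turns on a difference of this size. The planned disposition, exposure, patient-time and Kaplan-Meier outputs let a reader see how far early leaving matters. Tightening the provisos would leave the primary estimate as it is and add essentially nothing to what is reported. This is a fair trade-off in the evaluable set, with a gap in detail that analysts would fill sensibly, and no change follows.

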## **6 ANALYSIS VARIABLES**

### **6.1 Efficacy Variables**

Efficacy variables include clinical, radio-graphic and/or PSA assessments.

### **6.2 Safety Variables**

#### **6.2.1 Primary Endpoint**

The proportion of subjects in SRES with at least one confirmed seizure as adjudicated by the Independent Adjudication Committee (IAC) during the 4-month treatment duration.

An evaluable subject is defined as a subject with a confirmed seizure during the 4-month treatment period of the study or who completed at least 3 months (75%) of the planned treatment. Only an enrolled subject who discontinues the study before completing 3 months on treatment may be replaced at the discretion of the Sponsor, however, an enrolled subject who is discontinued due to a confirmed seizure event will not be replaced.

A cumulative summary to include all seizure events, including those occurring beyond the 4 month treatment period will be included.

In case the drop-out rate is higher than expected, appropriate method such as Kaplan-Meier estimations may be considered.

### 6.2.2 Other Safety Variables

Safety will be assessed by evaluation of the following variables:

- Treatment-emergent adverse events (TEAEs; frequency, severity, seriousness, and relationship to study drug).
- Clinical laboratory variables (hematology, biochemistry including liver function tests, and urinalysis)
- Vital signs (systolic and diastolic blood pressure and pulse rate)
- 12-lead electrocardiogram (ECG)

TEAE is defined as an adverse event observed after starting administration of the test drug/comparative drug. If the adverse event occurs on Day 1 and the onset check box is marked "Onset after first dose of study drug" or the onset check box is left blank, then the adverse event will be considered treatment emergent. If the adverse event occurs on Day 1 and the onset check box is marked "Onset before first dose of study drug", then the adverse event will not be considered treatment emergent. If a subject experiences an event both during the pre-investigational period and during the investigational period, the event will be considered as TEAE only if it has worsened in severity (i.e. it is reported with a new start date). All adverse events collected that begin within 30 days after taking the last dose of study drug will also be counted as TEAE.

A drug-related TEAE is defined as any TEAE with at least possible relationship to study treatment as assessed by the investigator or with missing assessment of the causal relationship.

### 6.3 Other Variables

- The duration of exposure

For each subject, the Length of Time on study drug will be calculated in days, using the following formula:

$$('Date\ last\ dose\ of\ study\ drug'^{\#} - 'Date\ first\ dose'^{*}) + 1$$

# = [End of study (EOS)-page of the Case Report Form (CRF)]

\* = 'date first study drug taken since last visit' [Visit 3-page of the CRF]

- Previous and concomitant medication

Previous medication is defined as medication with at least one dose taken before the date of the first dose of study drug.

Concomitant medication is defined as medication with at least one dose taken between the date of first dose (inclusive) and the date of last dose (inclusive) of study drug.

## **7 STATISTICAL METHODOLOGY**

### **7.1 General Considerations**

For continuous variables, descriptive statistics will include the number of subjects (n), mean, standard deviation, median, minimum and maximum. When needed, the use of other percentiles (e.g. 10%, 25%, 75% and 90%) will be mentioned in the relevant section. Frequencies and percentages will be displayed for categorical data. Percentages by categories will be based on the number of subjects with no missing data, i.e. will add up to 100%.

All data processing, summarization, and analyses will be performed using SAS® Version 9.1.3 or higher on Unix. Specifications for table, figures, and data listing formats can be found in the TLF specifications for this study.

For the definition of subgroups of interest please refer to section [7.8](#)

### **7.2 Study Population**

#### **7.2.1 Disposition of Subjects**

The following subject data will be presented:

- Number and percentage of subjects in each analysis set;
- Number and percentage of subjects completed and discontinued 4 month treatment period, by primary reason for treatment discontinuation;
- Number and percentage of subjects completed and discontinued the 1 year extension period, by primary reason for discontinuation; and

#### **7.2.2 Protocol Deviations**

Protocol deviations as defined in the study protocol (Section 8.1.6 Protocol Deviations) will be assessed for all enrolled subjects. The number and percentage of subjects meeting any criteria will be summarized for each criterion and overall, by total as well as by study site. Subjects deviating from a criterion more than once will be counted once for the corresponding criterion. Any subjects who have more than one protocol deviation will be counted once in the overall summary. A data listing will be provided by site and subject.

The protocol deviation criteria will be uniquely identified in the summary table and listing. The unique identifiers will be as follows:

- PD1 - Entered into the study even though they did not satisfy entry criteria,
- PD2 - Developed withdrawal criteria during the study and was not withdrawn,
- PD3 - Received wrong treatment or incorrect dose,
- PD4 - Received excluded concomitant treatment.

### **7.2.3 Demographic and Other Baseline Characteristics**

Demographic and other baseline characteristics will be summarized by descriptive statistics.

Number and percentage of subjects enrolled in each country and site will be presented for the SAF.

Medical history is coded in MedDRA, and will be summarized by System Organ Class (SOC) and Preferred Term (PT) as well as by PT alone for the SAF.

Baseline tumor burden will be summarized by body system.

Prostate cancer diagnosis and the categories of seizure risk will be summarized using frequencies.

### **7.2.4 Previous and Concomitant Medications**

Previous medications are coded with WHO-DD, and will be summarized by therapeutic subgroup (ATC 2nd level) and chemical subgroup (ATC 4th level) and preferred WHO name for the SAF.

As with previous medication, concomitant medication will be summarized by therapeutic subgroup (ATC 2nd level) and chemical subgroup (ATC 4th level) and preferred WHO name for the SAF. Subjects taking the same medication multiple times will be counted once per medication and investigational period. A medication which can be classified into several chemical and/or therapeutic subgroups is presented in all chemical and therapeutic subgroups.

Prostate cancer treatment history will be summarized.

## **7.3 Study Drugs**

### **7.3.1 Exposure**

The following information on drug exposure will be presented for the SAF:

- Descriptive statistics for average daily dose; and
- Number and percent of subject with dose increases, decreases or interruptions

Duration of exposure will be summarized in two ways.

- Descriptive statistics will be presented.
- Exposure time will be categorized according to the following categories:
  - less than 3 months
  - at least 3 month, less than 6 months
  - at least 6 month, less than 9 months
  - at least 9 month, less than 12 months
  - at least 12 month, less than 15 months
  - 15 months or more

- Unknown.

Counts and percentages of subjects in each of these categories will be summarized for the SAF.

### **7.3.2 Treatment Compliance**

Overall compliance will be examined for subjects in the SAF whose total study drug count and first and last days of treatment are known. The drug dispense records will be collected as a part of IVRS data.

Percent overall compliance will be summarized in two ways for the SAF:

- Descriptive statistics will be presented
- Percent compliance will be categorized according to the following categories:
  - less than 50%
  - at least 50%, less or equal to 75%
  - greater than 75%
  - Unknown.

The summaries described above will be provided for 4 month treatment period and entire study period separately.

## **7.4 Analysis of Efficacy**

Efficacy data will be collected at baseline and at the time of seizure event for this study. No statistical analysis will be conducted. Instead, disease assessments including clinical, radiographic and/or PSA assessments collected will be listed.

## **7.5 Analysis of Safety**

All analysis of safety will be presented for SAF, unless specified otherwise.

### **7.5.1 Analysis of Primary Endpoint**

#### **7.5.1.1 Primary Analysis**

Primary endpoint, the proportion of evaluable subjects with at least one confirmed seizure as adjudicated by the IAC during the 4-month treatment duration, will be estimated using point estimate and its 95% exact confidence interval using all SRES.

#### **7.5.1.2 Secondary Analysis**

The same analysis of the primary endpoint as described in 7.5.1.1 will be conducted for a cumulative proportion to include all seizure events, including those occurring beyond the 4 month-treatment period using all SRES. Incidence of seizure events, including only the first seizure event, per patient-time exposure will be summarized for SAF. Any subsequent seizure event(s) will be listed.

In addition, seizure event free rate at 4 months, 12 months, and 16 months will be calculated using Kaplan-Meier estimation if data permit in SAF.

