1.4 Risk-Benefit Assessment

In the Phase 3 study CRPC2 (AFFIRM), the pre-specified interim analysis at the time of 520 events demonstrated a statistically significant improvement in overall survival in patients with metastatic CRPC treated with enzalutamide versus placebo (hazard ratio [HR] = 0.631; 95% CI: 0.529, 0.752, $p < 0.0001$). Median survival was 18.4 months in the enzalutamide arm and 13.6 months in the placebo arm ($\Delta = 4.8$ months). The overall survival benefit was consistent across all subgroups, including age, baseline pain intensity, geographic region, and type of disease progression at entry. Enzalutamide treatment was superior to placebo for all secondary endpoints including proportion of patients with a reduction in PSA level by 50% or more (54% vs. 2%, $p < 0.001$), soft tissue response rate (29% vs. 4%, $p < 0.001$), quality-of-life response rate (43% vs. 18%, $p < 0.001$), time to PSA progression (8.3 vs. 3.0 months; HR 0.25, $p < 0.001$), radiographic PFS (8.3 vs. 2.9 months; HR 0.40, $p < 0.001$), and time to first skeletal-related event (16.7 vs. 13.3 months; HR 0.69, $p < 0.001$). Based on

the AFFIRM data, the US FDA approved enzalutamide in August 2012 for men with metastatic CRPC who previously received docetaxel therapy.

Review of the enzalutamide program safety information obtained through Jan 2014 confirmed that the previously identified potential risk of seizure is an “important identified risk” per International Conference on Harmonisation (ICH) definition, with an estimated incidence of <1% based on cumulative data. In addition to seizures, hypertension, falls, hallucinations, non-pathologic fractures, neutrophil count decrease, and Cognitive/memory impairment were defined as important identified risks

The confirmed benefit of enzalutamide in the randomized CRPC2 trial in terms of overall survival advantage over placebo indicates a favorable benefit risk profile even in patients who were systematically excluded from clinical studies and may be at potential increased risk of seizure described in this protocol.

This study will enroll metastatic CRPC patients who have at least one risk factor which has the potential to increase risk for seizure. All subjects will have a baseline neurology assessment prior to treatment initiation with enzalutamide.

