7.1 Sample Size

Approximately four hundred (400) subjects will be enrolled to target approximately 350 evaluable subjects, assuming a drop-out rate of approximately 13% for this population and based on the recommendation from the FDA, respectively. Assuming the true incidence of seizure in the first 4 months as 0.93%, based on the incidence rate of 2.8 per 100 patient years, which is obtained from the previous studies and the sample size of 350, the chance of observing 5 or less subjects with seizure events is 88.9%. Given 5 out of 350 subjects, i.e., point estimate of 1.43%, the upper limit 95% exact confidence interval will be 3.31% and the width of the exact confidence interval will be 2.84%.

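### The 12- and 16-month seizure-free rates rest on Kaplan-Meier with no rule for death; adding a cumulative incidence with death competing would correct a modest upward error

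*SAP*

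**What the plan says.** SAP 7.5.1.2 plans three summaries that reach beyond 4 months:

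- A "cumulative proportion to include all seizure events, including those occurring beyond the 4 month-treatment period using all SRES", with an exact confidence interval. The protocol synopsis sets its data cut-off at one year after the 4-month visit.
- A rate: "Incidence of seizure events, including only the first seizure event, per patient-time exposure will be summarized for SAF".
- Landmark probabilities: the "seizure event free rate at 4 months, 12 months, and 16 months will be calculated using Kaplan-Meier estimation if data permit in SAF".

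The primary 4-month proportion does not use Kaplan-Meier. Under SAP 7.5.1.1 it "will be estimated using point estimate and its 95% exact confidence interval using all SRES". Protocol 7.4.1.1 holds Kaplan-Meier in reserve if drop-out is high, "to efficiently estimate the proportion of seizure events with accounting for the censored observations in the SAF".

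Neither document mentions competing risks or cumulative incidence. Neither gives a censoring rule for death, treatment stop, a new anticancer therapy or roll-over. Deaths and seizures (all potential seizures are reported as serious adverse events, Protocol 5.5.2) are collected to 30 days after the last dose (Protocol 5.4.2 and Table 1, footnote i). Unequivocal progression removes a man from drug and study (Protocol 6.1).

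**The concern.** A man who dies without a seizure can no longer have one. Unless told otherwise, a Kaplan-Meier analysis of time to first seizure censors him at death, as if he remained at the same risk as the men still followed. Its complement then estimates the seizure risk that would apply if nobody died, which is higher than the probability of a seizure actually occurring.

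Mortality in this disease is not negligible over 16 months. Protocol 1.4 reports from an earlier phase 3 trial: "Median survival was 18.4 months in the enzalutamide arm and 13.6 months in the placebo arm".

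The other two summaries do not fill the gap. The patient-time rate does not carry this bias, but it is not a probability, and converting it by 1 − exp(−rate × time) returns to the no-death risk. The crude proportion counts men with incomplete follow-up as seizure-free, which tends to understate risk. The Kaplan-Meier rates are therefore the only planned landmark probabilities that allow for censoring, and a reader is likely to take their complement as the seizure risk by 12 or 16 months.

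**Working it through.** **Reproducing the plan's own figures.** The documents give no expected value at 12 or 16 months, so the nearest check is the sample-size statement. Protocol 7.1 takes its 4-month risk "based on the incidence rate of 2.8 per 100 patient years": 2.8/100 × 4/12 = 0.933%, stated as 0.93%. With n = 350 and p = 0.93%, the exact binomial probability of 5 or fewer events is 88.9%, as stated. The seizure rate can be used as an input.

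**Inputs**

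- Seizure hazard: λs = 0.028/12 = 0.00233 per month (Protocol 7.1).
- Exit from follow-up: median 8.3 months, the radiographic progression-free survival on enzalutamide in Protocol 1.4, used as a proxy for treatment stop. λx = ln 2/8.3 = 0.0835 per month.
- Share of exits that are seizure-free deaths: s = 5% to 30%. This is an assumption; the documents give no figure. Death hazard under observation: λd = s × λx = 0.0042 to 0.0251 per month.
- Constant hazards, with exits other than death independent of seizure.

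**Formulas**

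- Kaplan-Meier target: 1 − exp(−λs t).
- Cumulative incidence with death competing: λs/(λs + λd) × [1 − exp(−(λs + λd) t)].

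Example at 16 months, s = 30%: 1 − exp(−0.0373) = 3.66%. Against this, 0.00233/0.02739 × [1 − exp(−0.4382)] = 0.0852 × 0.3548 = 3.02%.

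| Month | 1 − KM | Cum. incidence, s = 5% | Gap (points), ratio | Cum. incidence, s = 30% | Gap (points), ratio |
|---|---|---|---|---|---|
| 4 | 0.93% | 0.92% | 0.008, 1.01 | 0.88% | 0.045, 1.05 |
| 12 | 2.76% | 2.69% | 0.068, 1.025 | 2.39% | 0.375, 1.16 |
| 16 | 3.66% | 3.55% | 0.119, 1.03 | 3.02% | 0.642, 1.21 |

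**Ceiling.** Let men under observation die at the full overall-survival rate: λd = ln 2/18.4 = 0.0377. Cumulative incidence is then 2.22% at 12 months (ratio 1.24) and 2.76% at 16 months (ratio 1.33, gap 0.91 points). Doubling or tripling the seizure rate leaves the 16-month ratio at 1.33 and 1.32 (7.20% against 5.42%; 10.60% against 8.00%).

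**Precision.** A Greenwood-type approximation for 400 men gives SE = S(t) × √{λs/[400(λs + h)] × [exp((λs + h)t) − 1]}, where S(t) = exp(−λs t) and h is the exit hazard. At 16 months this is 1.4 points with h = 0.0835 and 1.1 points with h = 0.0377. The gap of 0.12 to 0.64 points is below one standard error.

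**Treatment stop.** If every exit were treated as competing, the 16-month figure would be 2.03% against 3.66%. That answers a different question, the share of men who have a seizure before leaving observation. It shows that treatment stop, rather than death, is probably the main reason for later censoring.

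**The case against.** The case against acting has real weight.

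- *The Kaplan-Meier rate may be what is wanted.* The SAP calls it a seizure-free rate, not the proportion of men with a seizure, and a hypothetical no-death risk is a legitimate target. The protocol's wording about estimating a proportion concerns the 4-month fallback. This stands. The SAP does not state which target it intends, so the remedy should keep Kaplan-Meier and add to it.
- *Censoring at death is inferred.* This also stands: no censoring rule is written. Censoring is the default reading, and the missing rule itself needs filling.
- *The added estimate is still partly hypothetical.* If treatment stops remain censored, it describes risk had men stayed on treatment while dying at the on-treatment rate. This limits how it may be labelled.
- *The error is small and lies on the cautious side for a safety study.* True. That sets the priority low, but the error is systematic and grows with time.

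A reader might also infer more than the documents support. One inference is that later seizure risk is assessed by Kaplan-Meier alone; SAP 7.5.1.2 also plans the rate and the crude proportion. Another is that the 16-month figure will be a third too high. That needs all deaths to fall under observation, although deaths later than 30 days after the last dose are not collected and progression ends participation. It also borrows 18.4 months from a trial in men previously treated with docetaxel, whereas this study does not require prior chemotherapy. Finally, Protocol 1.1 plans no direct comparison with external data; it says only that results will be interpreted in their context.

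**Conclusion.** The point holds as a cheap improvement to a supplementary analysis. With deaths censored by default, 1 minus Kaplan-Meier overstates the probability of actually having a seizure on treatment by about 3% to 16% at 12 months and 3% to 21% (0.12 to 0.64 points) at 16 months. The direction follows from the method. The size rests on constant hazards, 2.8 seizures per 100 patient-years, exits at a median of 8.3 months and the assumed 5% to 30% share of deaths among exits. An excess of 33% at 16 months is a ceiling, not an expectation.

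The primary endpoint is untouched. Even if the protocol's Kaplan-Meier fallback were used at 4 months, the gap would be only 0.008 to 0.045 points under the same assumptions.

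**What to change.** In SAP 7.5.1.2, beside each Kaplan-Meier rate at 4, 12 and 16 months in the SAF, add the Aalen-Johansen cumulative incidence of first confirmed seizure with a 95% confidence interval and the number at risk. State the rules in the same place: seizure-free death is the competing event, and other ends of follow-up (treatment stop plus 30 days, new anticancer therapy, roll-over) are censored.

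Label the new figure as the on-treatment seizure risk allowing for death, and do not report it as the proportion of all treated men who have a seizure. Keep Kaplan-Meier, described as the hypothetical seizure-free rate.

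The cost is a short SAP addition and one extra row per landmark. The deaths needed are already collected to 30 days after the last dose and counted in the adverse-event overview (SAP 7.5.2). The downside is one more estimate to explain.
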